#### 6.1.8 Use error

According to EN ISO 14155, **Use Error** is any act or omission of an act that results in a different medical device response than intended by the manufacturer or expected by the user.

NOTE 1: User error includes slips, lapses, and mistakes.

**NOTE 2:** An unexpected physiological response of the subject does not in itself constitute a use error.

#### 6.2 Evaluation

Adverse events experienced in this study may be associated with the study device (i.e., ADE) or the study procedures described in this protocol.

When evaluating AEs, the Investigator must determine if the event is serious, according to the definitions in 6.1.6, and assess the severity of symptoms and evaluate the relationship of the event to the study device and study protocol, using the following guidelines:

#### Severity

- Mild: Subject awareness of a sign or symptom that is easily tolerated, requires no treatment, and does not interfere with the subject's daily activities
- Moderate: Subject awareness of a sign or symptom which may be a low level of concern to the subject and may interfere with daily activities, but can be relieved by simple therapeutic care
- Severe: A sign or symptom that interrupts the subject's daily activity and requires systemic therapy or other treatment

#### Relationship (Causality) to Study Device or Study Protocol

- Not Related: AEs which are clearly and incontrovertibly due to causes other than the study device or study protocol (e.g., concomitant disease, etc.)
- Related: AEs which are felt with a reasonable degree of certainty to be related to the study device or study protocol
- Unknown: AEs for which a connection with the study device or study protocol cannot be ruled-out with certainty, or not enough information is available to assess the relationship

#### 6.3 Reporting

#### 6.3.1 On-Site Expedited Reporting

The Investigator is obligated to report the following to the Sponsor within 24 hours of becoming aware of the event to ensure the safety of all participants in the study and to meet regulatory reporting requirements:

- all SAEs, regardless of relationship to study device or study protocol
- all **non-serious AEs** determined to be related to the study device (ADE)

- all device deficiencies that do not result in one of the above reportable events
- all secondary surgical interventions (removal, replacement or repositioning) involving the study lens

In addition, the following events are to be reported to the Sponsor as SAEs in this study:

- endophthalmitis
- pupillary block
- retinal detachment
- stromal thinning/corneal melting
- ≥2 lines BCDVA loss not secondary to any underlying condition after 3 months postoperative

All SAEs/ADEs and device deficiencies will be reported via the eCRF. The required information will be sent to the safety department of the CRO and the Sponsor automatically. Telephone, fax and e-mail can be used for initial reporting if there are difficulties accessing the eCRF. The contact details of the safety department of the CRO are:

All SAEs will be reported by the CRO on behalf of STAAR Surgical to the Competent Authorities of the involved countries according to the EU regulations and the national legislations.

The Sponsor is to report a SAE or a new finding to it which indicates an imminent risk of death, serious injury, or serious illness and that requires prompt remedial action for other subjects or a new finding to it to the regulatory authority immediately but not later than 2 calendar days of awareness of the event.

The Sponsor is to report any other SAE or a new finding/update to it immediately, but not later than 7 calendar days following the date of awareness of the event.

In addition, the CRO will report SAEs to the responsible EC without undue delay, if applicable according to national regulations. The CRO is responsible for checking what reporting procedures are applicable for his/her EC regarding SAEs and final report of the outcome of the study and to comply with such reporting procedures during the study period.

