Presbyopia is a condition associated with the expected age-related decline in near-focusing ability that becomes manifest at approximately age 45. Presbyopia affects all people, regardless of their underlying refractive error. Those who are farsighted prior to the onset of presbyopia will likely experience difficulty with near vision at a somewhat younger age, while those who are nearsighted may not notice the onset of presbyopia until somewhat later. Regardless, all people will eventually require optical correction in addition to any distance correction for near vision tasks such as reading.

Presbyopia is associated with reduced health-related quality of life, and presbyopia corrected with glasses is associated with a nominal decrease in quality of life, similar to that of treated systemic hypertension. Approximately 10% of presbyopic patients suffer such inconvenience from spectacle correction that they would consider surgical intervention.

Individuals who have had refractive surgery such as LASIK for correction of their distance vision will still experience presbyopia when they reach their mid-forties. Monovision, the intended correction of one eye for near vision and the fellow eye for distance vision, represents a common strategy for addressing presbyopia in older patients undergoing LASIK. Intraocular lens (IOL) implants intended for use at the time of cataract surgery have also been used to provide monovision. While monovision correction of presbyopia is related to some improvements in health-related quality of life, the quality of life with monovision is still worse than the quality of life for younger subjects with emmetropia. Specific presbyopia-correcting IOLs have also been developed incorporating multifocal and EDOF optical elements intended to provide simultaneous vision at near and far distances. While monovision LASIK, multifocal IOLs and corneal implants have been developed to improve near vision, these methods typically result in some expected degradation of distance vision and unwanted optical side effects such as halos and glare in order to gain an improvement in uncorrected near vision.

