# 6.0 ADVERSE EVENT REPORTING

Throughout the course of this study, all efforts will be made to remain alert to possible AEs. If an AE occurs, the first concern will be the safety of the subject, and appropriate medical intervention will be made. All ocular AEs and all SAEs (both ocular and non-ocular) will be reported by the Investigator in this study. Non-serious non-ocular AEs will not be documented in the eCRF. The collection of AEs begins at the time the subject completes the informed consent process to participate in the study.

All device-related AEs and SAEs reported in this study will be reviewed by the responsible Medical Monitor and forwarded to STAAR Complaint Handling department. In addition, all other events that meet the definition of a product complaint (i.e., device deficiency) will be evaluated and investigated in accordance with STAAR's complaint handling procedures.

Refer to Section 6.3.1 for instructions on events that require expedited reporting to the Sponsor.

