#### **Exploratory analysis:**

All additional variables will be summarized by summary statistics for continuous variables (including number of non-missing values, mean, SD, median, minimum, maximum) and frequency (N, %) for discrete variables.

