#### Surgical Technique/Directions for Use

- 1. Open the package and verify the correct lens model, dioptric power and overall diameter.
- 2. Inspect the lens vial to ensure it is not damaged. Verify that the level of the liquid fills at least 2/3 of the vial. The thermoform tray and vial should be opened in a sterile field.
- 3. While keeping the vial in a vertical position, remove the aluminum seal and remove the cap.
- 4. Carefully remove the lens from the vial.
- 5. Handle the lens by the haptic portion. Do not grasp the optic with forceps as this could potentially lead to damage to the smooth anterior and posterior optical surfaces.
- 6. The lens should be carefully examined under the microscope for damage or particulate matter prior to implantation.
- 7. The lens should not be exposed to any solutions other than the normally used intraocular irrigating solutions (e.g., BSS, viscoelastic, etc.)
- 8. Do NOT let the lens dry after removal from the glass vial. It is recommended that the ICL be held in sterile BSS solution prior to implantation.
- 9. The ICL should be handled carefully. No attempt should be made to reshape or cut any portion of the lens. Do not apply undue pressure to the ICL optical portion with a sharp object since this could perforate the optic.
- 10. The recommended incision size is 3.5 mm or less.
- 11. Low molecular weight (2% hydroxypropyl methylcellulose) viscoelastic should be used during loading of the injector system, as well as in the anterior chamber to protect the structures of the eye during the procedure.
- 12. Utilize only the MICROSTAAR injector MSI-PF or MSI-TF reusable injector with SFC-45 single-use cartridge and FTP provided to insert the lens in the folded state.
- 13. The lens should be injected within 1-2 minutes after loading.
- 14. Never touch the center of the optic with instruments once the lens is placed inside the eye. Inadvertent pressure through the optic could potentially damage the central crystalline lens resulting in lens opacity.

- 15. The intended location of the lens is behind the iris within the posterior chamber and in front of the anterior capsule of the crystalline lens.
- 16. Complete irrigation and aspiration of the viscoelastic from the eye after completion of the surgical procedure is essential. Inadequate flushing of the viscoelastic from the eye may lead to IOP spikes. Viscoelastic products that may be difficult to aspirate should not be used.

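### The planned outputs cannot state how many implanted eyes lost two or more lines of best-corrected distance acuity (BCDVA) from any cause

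*Combined protocol and SAP*

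**What the plan says.** **Reporting.** Section 6.3.1 sets a general duty to report "all SAEs, regardless of relationship to study device or study protocol". It then adds a list, introduced by "In addition, the following events are to be reported to the Sponsor as SAEs in this study", and one item of that list is "≥2 lines BCDVA loss not secondary to any underlying condition after 3 months postoperative". No section says what counts as an underlying condition. Section 6.0 is broader: "All ocular AEs and all SAEs (both ocular and non-ocular) will be reported by the Investigator in this study".

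**Safety analysis.** The safety endpoint (Section 7.2.2) is the rate of ocular AEs in implanted eyes, with no target. The safety paragraph of Section 7.5 tabulates AEs by system organ class, preferred term, intensity and relationship to the lens. It names no table of acuity loss.

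**BCDVA.** Tables A1 and A2 schedule BCDVA before surgery and at Visits 3, 4 and 5 for each eye. Section 3.2.3 gives it as an example of a safety measure to record after explantation. It is not among the endpoints in Section 7.2, so it falls under the exploratory paragraph of Section 7.5: "All additional variables will be summarized by summary statistics for continuous variables", namely N, mean, SD, median, minimum and maximum.

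**Analysis sets.** Safety analyses use the SES and FAS; analyses beyond performance and safety use the FAS and PPS. The SES holds every implanted eye. The FAS holds only those SES eyes that have data for the primary endpoint.

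**The concern.** Every eye enters with BCDVA of 20/20 or better (inclusion criterion 8) and receives an elective implant, so distance acuity lost is a basic safety question. The protocol itself points to it. The introduction says of other near-vision methods (monovision LASIK, multifocal IOLs, corneal implants) that "these methods typically result in some expected degradation of distance vision and unwanted optical side effects such as halos and glare". Appendix B warns of a route by which the surgery could harm the natural lens: "Inadvertent pressure through the optic could potentially damage the central crystalline lens resulting in lens opacity".

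Against that background, one would expect a count of eyes that lost acuity. The plan offers three partial substitutes:

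- **The 6.3.1 criterion** is restricted by an undefined exclusion and by time since surgery.
- **The AE tables** depend on whether, and under which term, an investigator reports a loss.
- **The descriptive summary** does not count eyes above any threshold, and it leaves out eyes without the primary outcome.

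At stake is whether the report can say, for all implanted eyes, how many were left with materially worse best-corrected distance vision.

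**Working it through.** The documents give no figure for BCDVA loss, so there is none to reproduce. The check is to ask of each planned output whether it yields the number of implanted eyes that lost 2 or more lines.

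**1. The 6.3.1 criterion.** It yields the count only for losses that meet the exclusion, whatever that term covers, and that occur after 3 months. Three months is about 13 weeks. Visit 3 (weeks 3 to 5) lies before that point, and Visit 4 (weeks 10 to 14) straddles it.

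**2. The AE tables.** No rule says at what measured loss BCDVA becomes an AE, or that a loss with a known cause is coded as vision loss as well as under its cause. A loss explained by lens opacity could appear under opacity alone, under vision loss alone, or under both. The preferred-term counts therefore cannot be relied on to give the number.

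**3. The descriptive summary.** Assumptions: change is follow-up minus baseline in logMAR, so positive is worse; 2 lines are 0.20 logMAR and one letter is 0.02. The counts of losing eyes are illustrative. The 96 eyes are the planned enrolment (Section 7.3).

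- Five eyes lose 0.20 and 91 gain 0.02: mean = (5 × 0.20 − 91 × 0.02)/96 = (1.00 − 1.82)/96 = −0.0085, a net gain. Median −0.02, minimum −0.02, maximum +0.20.
- One eye loses 0.20 and 95 gain 0.02: mean = (0.20 − 1.90)/96 = −0.0177. Median −0.02, minimum −0.02, maximum +0.20.

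Median, minimum and maximum are identical for one losing eye and for five. The means differ by 0.0092 logMAR, or 0.0092/0.02 = 0.46 of a letter. The SD would rise, but it cannot be turned into a count unless the spread of the other eyes is known.

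If instead all other eyes are unchanged, the mean shift is k × 0.20/n. The rate k/n has these exact (Clopper-Pearson) 95% limits:

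| Losing eyes / n | Mean shift (logMAR) | Rate | 95% limits |
|---|---|---|---|
| 1/86 | 0.002 | 1.2% | 0.03% to 6.3% |
| 3/86 | 0.007 | 3.5% | 0.7% to 9.9% |
| 5/86 | 0.012 | 5.8% | 1.9% to 13.0% |
| 5/96 | 0.010 | 5.2% | 1.7% to 11.7% |

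With no losing eyes among 86, the upper limit is 4.2%. All these limits treat eyes as independent. With two eyes per subject and correlation ρ between them, the variance is multiplied by 1 + ρ. For ρ from 0 to 1 the standard error grows by a factor of up to √2 = 1.41.

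**4. Who is summarised.** Section 7.3 enrols 96 eyes to have 86 after attrition, so 96 − 86 = 10 eyes (10/96 = 10.4%) may lack primary-endpoint data by the plan's own allowance. Those eyes are in the SES but not in the FAS. An eye explanted before Visit 5 could be among them. Because the BCDVA summary is set in the FAS and PPS, even its maximum may miss the worst eye.

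**The case against.** A reader might infer that the 6.3.1 exclusion keeps implant-caused losses out of the safety results. The documents do not support that. The item belongs to an additional list for expedited reporting; it neither defines the safety endpoint nor limits the safety analysis. All ocular AEs are reported whatever their cause. Section 6.1.1 includes procedure-related events, and its list of expected findings with restricted reporting contains neither BCDVA loss nor lens opacity. Corneal edema from Visit 3 and raised IOP above the stated thresholds are reportable. A permanent impairment, or an intervention to prevent one, can be an SAE under Section 6.1.6, and device-related non-serious AEs are reported within 24 hours. Nor does the text say that implant-induced opacity is an underlying condition; the term can equally mean disease independent of the implant.

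Four further objections have weight:

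- BCDVA is not merely averaged: median, minimum and maximum are planned, and Section 7.0 allows shift tables for qualitative variables where applicable.
- Section 7.0 leaves details to a SAP. The combined document contains no separate SAP text, so a BCDVA-loss table there cannot be ruled out.
- The introduction's remark concerns other methods and predicts nothing about this lens.
- The illustrative counts are chosen, not observed.

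All of this stands, and it limits the point to what the stated outputs can show. It does not supply the count. Open-ended AE reporting sets no acuity threshold, the maximum describes one eye, and no shift table is specified for BCDVA.

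**Conclusion.** The point holds in this limited form: the plan as written describes no output from which the number of implanted eyes losing 2 or more lines of BCDVA, from any cause, can be read. No underreporting of AEs is shown, and no downward bias in a planned rate can be claimed, because the plan defines no rate of BCDVA loss.

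The size can only be illustrated. Under the assumed counts, a 5.2% rate of 2-line loss (limits 1.7% to 11.7%, ignoring pairing) coexists with a mean change of -0.009 logMAR in the favourable direction. Separately, up to 10 of 96 implanted eyes may be absent from the BCDVA summary under the plan's own attrition allowance. This assumes that BCDVA is handled as an additional variable in the FAS and PPS, which is how Section 7.5 reads, and that no SAP text adds the table.

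This is a worthwhile improvement to safety reporting. The primary endpoint, the two-stage design and the sample size are unaffected.

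**What to change.** **Section 7.5, safety analysis.** Add a table in the SES of the number and percentage of implanted eyes with a BCDVA loss of 2 or more lines from baseline, at Visits 3, 4 and 5 and at the last available visit, regardless of cause. State the definition of a line in logMAR or letters, show the number of eyes with missing BCDVA at each visit, and flag values taken after explantation. List the recorded cause for each such eye. Give 95% limits that allow for two eyes per subject, for example by an effective sample size based on the between-eye correlation. A simpler supplement is the number of subjects with at least one such eye, with exact limits.

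**Section 6.3.1.** The sponsor should reconcile the undefined underlying-condition wording with the general definitions in Sections 6.1.1 and 6.1.6 and state what it covers. No clinical reporting rule is proposed here.

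**Cost.** One extra table from measurements already scheduled, plus a clarifying clause. The downside is that the reported loss rate may look less favourable than the summary statistics alone.

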#### 6.3.2 Safety Reporting within the European Economic Area

In Germany, reporting will be done according to Act on Medical Devices (MPG) and German Safety Plan for Medical Devices (MPSV, Section 3 sub-section 6) by using the current reporting form available on the BfArM homepage. Investigators have to report all SAEs to the Sponsor immediately. The Sponsor of a clinical trial of a medical device that is conducted in Germany (and other countries) has to report SAEs to BfArM immediately or quarterly, depending on the following conditions:

Condition for reporting to BfArM	Country of occurence	Timeline for reporting to BfArM	Report type, form
A causal relationship between the SAE and the investigational medical device, a comparator device, diagnostic or therapeutic procedures performed as part of the clinical trial or other conditions of the trial conduct cannot be excluded	Germany	Immediately	Single report, SAE report form
	All other countries where the clinical trial is performed	Immediately	Summary table, SAE report table All SAEs shall be documented using the same Excel file, in a cumulative manner, using the same Excel sheet
A causal relationship between the SAE and the investigational medical device, a comparator device, diagnostic or therapeutic procedures performed as part of the clinical trial or other conditions of the trial conduct can be excluded	All	Quarterly	Summary table, SAE report table
All SAEs	All	Quarterly	SAE summary evaluation

Regardless of the criteria mentioned in the table, the Sponsor must report all SAEs occurring in Germany to the competent authorities of other contractual states of the Agreement on the European Economic Area immediately if the clinical trial is also being performed in those countries.

## 6.3.3 Off-Site SAE Reporting

When participating in multicenter clinical trials, Principal Investigators may receive "off-site" reports (e.g., SAE Report). These are Sponsor reports of SAEs which occurred at other sites for the same trial, or in different trials using the same test article, that met the criteria for reporting to a regulatory agency. These should be reported to the reviewing EC per their established reporting procedures. The EC may require a revision to the ICF and reconsenting of patients if the SAE provides new information regarding risk to the study subject.

#### 6.3.4 Reporting of Complaints for STAAR Surgical Products

Refer to Section 6.1.1 and 6.3.1 for instruction on reporting of product complaints that meet the definition of AEs/SAEs and ADEs that occur during the study.

All information collected on a CRF could potentially be identified as a product complaint, as defined in Section 6.1.3. The Sponsor has identified what information collected under this study could potentially be identified as a complaint. During clinical monitoring by the Sponsor/designee, the information collected on the CRFs will be evaluated to determine if any of the information should be forwarded to the Sponsor for consideration as a complaint. The Sponsor has the responsibility for evaluating and investigating potential complaints in accordance with STAAR's internal complaint handling procedures.

Any complaints, malfunctions or similar events related to ancillary STAAR Surgical marketed products used in this study should be reported by the Investigators in accordance with the reference information provided on the commercial packaging.

#### 6.3.5 Adverse Events and SAEs at Subject Exit

Ongoing ocular AEs at study exit will be documented as such in the CRFs and followed per the Investigator's standard of care.

Ongoing SAEs and ADEs will be followed until resolution or no further change in the condition is expected. Non-serious AEs that are ongoing at the study exit visit or upon discontinuation from the study will be followed per the Investigator's standard of care. Documentation in the eCRF of this follow-up is not required although subject care should continue as appropriate.

# 7.0 STATISTICAL METHODS

This section describes the statistical analyses intended at the time of investigation planning. Further details on the statistical and analytical aspects will be presented in the Statistical Analysis Plan (SAP).

Any deviations from planned analyses, the reasons for such deviations, and all alternative or additional statistical analyses that may be performed before database close will be described in amendments to the clinical protocol or the SAP. All deviations and/or alterations will be summarized in the clinical study report.

Continuous variables (values and changes from baseline) will be summarized by N, mean, SD, median, minimum, and maximum. For qualitative variables, absolute and percent frequencies (N, %) and, if applicable, shift tables will be displayed. Confidence limits will be given where appropriate.

